## The Inorganic Nitrate for Exercise in Heart Failure (iNIX-HF) Trial

### **Protocol #1**

**Protocol version #14**

**Date: 01/07/2020**

**ClinicalTrials.gov: NCT02797184**

**Principal Investigators: [name] and [name]**

### **Background:**

Heart Failure (HF) is a major public health problem when considering the incidence, prevalence, mortality rate, and costs to the patient and the health care system. According to the American Heart Association (AHA), it is estimated that there are over 5.1 million people in the United States (US) and 23 million people worldwide affected by HF. One in nine deaths is due to heart failure, and 50 percent of people who have heart failure will die within the first 5 years of diagnosis. HF costs the healthcare system in the US \$32 billion dollars annually in missed workdays, medications, and health care services. A contributing factor to this cost is that surviving patients with heart failure have a higher burden due to the debility HF causes compared to those without heart failure. The debility is so profound that the New York Heart Association classification system of HF is based on the severity of the patient's inability to exercise and perform activities of daily living. Given the disabling nature of HF and its impact on both the patient as well as the healthcare system, any improvement in exercise capacity or tolerance would be of benefit.

There is emerging data from our group and others that dietary nitrate, particularly in nitrate-rich foods such as beetroot juice (BRJ), increases plasma NO3 levels, plasma NO2 levels, and breath NO levels. This increase in NO improves exercise performance even in patients with HF. This improvement in performance is due to several physiologic effects of NO. It is a vasodilator and helps improve muscle perfusion. NO also increases muscle power and speed of contraction through its actions on cGMP. Thus, dietary *INORGANIC* nitrate in beetroot juice appears to be a novel treatment with which to attack the disabling effects of heart failure.

Unfortunately, BRJ has potential unwanted side effects, which might limit its use on a large scale. First, the taste is bitter, earthy, and salty. One reviewer of a grant even remarked that it was "unfit for human consumption". Second, the juice can cause beeturia and red-colored stools, which may make patients think they are bleeding or may mask true internal bleeding. Next, beetroot juice is high in oxalate; thus, its chronic consumption may increase kidney stone formation. Lastly, it is administered as 2/3 of a cup of liquid, so it is by nature less portable. Thus, there is a clear need for a new form of delivery for inorganic nitrate for patients with HF.

Therefore, potassium nitrate (KNO3) is an intriguing alternative for delivery of inorganic nitrate to subjects with HF. Dietary inorganic nitrate in KNO3 as a source of NO has several advantages over the classical nitric oxide synthase production pathway (L-arginine), current pharmacologic *ORGANIC* nitrates, sildenafil, and beetroot juice (see Table 1. below). Ten mmol of pharmacy-grade KNO3 can be put into a single gelatin capsule (gelcap) by the Barnes-Jewish compounding

## The Inorganic Nitrate for Exercise in Heart Failure (iNIX-HF) Trial

pharmacy. This is roughly the equivalent of two-thirds of a cup of beetroot juice. The gelcap would be devoid of taste, is portable, does not contain oxalate, and would not cause beeturia or red stools. We also believe that these advantages of  $\text{KNO}_3$  will increase medication compliance.

**Table 1.  $\text{KNO}_3$  versus other possible approaches for increasing NO**

Current Approaches	Advantages of $\text{KNO}_3$
L-arginine	

• Not dependent on NO synthase (NOS)

• Functions well in acidic tissues

• Functions well in ischemic tissues

Organic, pharmacologic nitrates (e.g., nitroglycerin)	

• Does not cause tolerance

• Does not increase reactive oxygen species (ROS) in mitochondria

• May be less likely to cause hypotension

• May be less likely to cause headaches

Sildenafil	

• Inadvertent inhibition of PDE6 is thought to be responsible for retinal dysfunction and vision changes

• May be less likely to cause hypotension

• May be less likely to cause flushing or headache

Beetroot juice	

• Does not contain oxalate (decreased risk of kidney stones)

• No allergies

• No bitter taste

• Easier to control exact nitrate content

• More portable

• No beeturia to be confused with/mask renal/urinary tract disease

• No red stool to be confused with/mask gastrointestinal disease

### **Study Aims:**

**Aim 1:** To determine the optimum dose of inorganic nitrate to improve exercise performance (i.e., aerobic capacity and muscle power) in patients with heart failure and reduced ejection fraction (HFrEF). Aerobic capacity will be assessed by peak oxygen consumption ( $\dot{\text{V}}\text{O}_{2\text{peak}}$ ) and muscle power will be assessed as maximal knee extensor power using a Biomedex machine. This is a double-blind, cross-over study aim in which each participant will receive single doses of potassium nitrate (10 or 20 mmol  $\text{KNO}_3$ ) administered in gelatin capsules in random order one week apart.

**Aim 1 Sub-Study: Pharmacokinetics.** To determine the time course of effects of a single 10 mmol dose of  $\text{KNO}_3$  on plasma nitrate and nitrite concentrations, breath nitric oxide concentration, blood pressure, and heart rate at rest. Blood samples will be drawn before dosing, every hour for 3 hours after  $\text{KNO}_3$  ingestion, and at 4.5, 6, 12, 18 (optional), and 24 hours post-dose. Plasma levels of nitrate and nitrite will be quantified using HPLC.

## The Inorganic Nitrate for Exercise in Heart Failure (iNIX-HF) Trial

**Aim 2:** To determine the effects of 2 weeks of inorganic nitrate therapy vs. placebo on aerobic capacity and muscle power in patients with HFrEF. The dose for this aim will be 10 mmol of  $\text{KNO}_3$  daily in a single gelatin capsule taken in the morning. This dosing regimen is based on the results of Aim 1, which revealed that the beneficial effects on exercise performance were not statistically different for the 10 and 20 mmol doses taken on one occasion in the morning, whereas tolerability was lower with the 20 mmol dose. The rationale for taking the 10 mmol dose once daily is based on the half-life of  $\text{KNO}_3$ .

**Aim 3:** To determine the effects of 6 weeks of inorganic nitrate therapy vs. placebo on aerobic capacity and muscle power in patients with HFrEF. The dose for this aim will be 10 mmol of  $\text{KNO}_3$  daily in a single gelatin capsule taken in the morning. This dosing regimen is based on the results of Aim 1, which revealed that the beneficial effects on exercise performance were not statistically different for the 10 and 20 mmol doses taken on one occasion in the morning, whereas tolerability was lower with the 20 mmol dose. The rationale for taking the 10 mmol dose once daily is based on the half-life of  $\text{KNO}_3$ .

### Participants:

**Inclusion:** Subjects included in this study will be patients  $\geq 18$  years of age with documented stable, NYHA class II-IV, non-ischemic heart failure with an ejection fraction  $<45\%$ . Participants must be on a stable medical regimen that is considered standard of care for HF (e.g., a beta-blocker and ACE-inhibitor/angiotensin receptor blocker) for at least 60 days prior to study. This is required to exclude any patients with reversible causes of cardiac dysfunction. All subjects must be free of any significant orthopedic limitations or other contraindications to strenuous exercise.

**Exclusion:** Vulnerable populations as defined by the U.S. Department of Health and Human Services, including prisoners and children, will be excluded from this study, as will be women who are pregnant. Those taking pharmacologic (organic) nitrates during the last 3 mo will be excluded, as will be those taking phosphodiesterase inhibitors (e.g., Viagra), as these can potentiate NO effects. Those taking proton pump inhibitors, antacids, or xanthine oxidase inhibitors will be asked to hold these medications for the duration of the study, if approved by his/her physician. These drugs will also be held for at least 5 half-lives before any study-related activity. Otherwise patients taking these drugs will be excluded as these can affect reduction of  $\text{NO}_3^-$  and  $\text{NO}_2^-$ . Subjects having active angina/ischemia from epicardial coronary disease, requiring supplemental  $\text{O}_2$  at rest or for exercise, will be excluded. Similarly, subjects with systolic blood pressure  $<95$  or  $>180$  mmHg or diastolic blood pressure  $<40$  or  $>95$  mmHg at consent, a plasma  $\text{K}^+$  level  $\geq 5\text{mEq/L}$ , or an estimated glomerular filtration rate of  $<45\text{ mL/min}$  based on most recent clinical laboratories will be excluded. Subjects with primary hypertrophic cardiomyopathy, infiltrative cardiomyopathy (e.g., amyloid), active myocarditis, complex congenital heart disease, active collagen vascular disease, more than mild mitral or aortic stenosis, valvular heart disease with severe regurgitation of any valve, or who have undergone percutaneous coronary intervention, new bi-ventricular pacing, or coronary bypass grafting in the last 3 mo will be excluded. Subjects with acute or chronic severe liver disease as evidenced

## The Inorganic Nitrate for Exercise in Heart Failure (iNIX-HF) Trial

by encephalopathy, INR>1.7 without anticoagulant therapy, or variceal bleeding will be excluded. Subjects with a terminal disease other than HF with expected survival <1 y will be excluded. Finally, subjects with any major orthopedic, psychiatric, neurological, or other condition that would impair performance of the exercise studies will be excluded.

### **Methods:**

#### **Aim 1: Dose Response of Potassium Nitrate (KNO3)**

The effects of a two different, single doses of KNO3 on  $\dot{V}O_2$ peak and maximal muscle power in patients with HFrEF will be evaluated during 2 study visits. The screening visit may be conducted as a separate visit or combined with the first dose visit.

#### **Screening Visit.**

- 1) **Consent:** All study procedures will be reviewed with the participant before he/she provides written informed consent. Consent includes giving permission for the investigators to review their medical records.
- 2) **Blood Sample:** A blood sample will be drawn for basic screening laboratories, including glucose and creatinine (for estimation of glomerular filtration rate).
- 3) **Physical Exam:** Subjects will have a brief history and physical examination. These will not be done with participants who have had a physical exam within the past 6 months.
- 4) **Resting Echocardiogram:** A resting echocardiogram will be performed to enable assessment of cardiac blood flow. An intravenous contrast agent may be used to obtain a clearer assessment of cardiac blood flow, if needed. The echocardiogram may not be necessary if the participant had an echocardiogram within the past 12 months.
- 5) **Questionnaires:** Subjects will be asked to complete two questionnaires: Basic Health Questionnaire and the Minnesota Living with Heart Failure Questionnaire.
- 6) **Instructions for KNO3 dose visits:** Subjects will be instructed to refrain from using mouthwash, antacids, proton pump inhibitors, or chewing gum before each KNO3 dose visit.

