### Screening Visit

- 1) **Consent:** All study procedures will be reviewed with the participant before he/she provides written informed consent. Consent includes giving permission for the investigators to review their medical records.
- 2) **Blood Sample:** A blood sample will be drawn for basic screening laboratories, including glucose,  $\text{K}^+$ , and creatinine (for estimation of glomerular filtration rate).
- 3) **Physical Exam:** Subjects will have a brief history and physical examination. These will not be done with participants who have had a physical exam within the past 6 months.
- 4) **Resting Echocardiogram:** A resting echocardiogram will be performed to enable assessment of cardiac blood flow. An intravenous contrast agent may be used to obtain a clearer assessment of cardiac blood flow, if needed. The echocardiogram may not be necessary if the participant had an echocardiogram within the past 12 months.
- 5) **Questionnaire:** Subjects will be asked to complete a Health Questionnaire.
- 6) **Instructions to participants:** Subjects will be instructed to refrain from using mouthwash, antacids, proton pump inhibitors, or chewing gum before the  $\text{KNO}_3$  dose visit.

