#### **Screening Visit.**

The screening visit procedures will be the same as for Aim 1 above. If a subject participated in Aim 1, then he/she will not have to repeat the screening procedures for Aim 2.

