#### **Exercise Testing Visit 1.**

- 1) Subjects will report to the Clinical Translational Research Unit (CTRU) at Washington University.
- 2) **Blood Samples:** Subjects will have blood drawn (20mL or about 1.5 tbsp) to determine blood levels of nitrate and nitrite using HPLC. A sample also will be obtained for measurement of potassium and blood lipids.
- 3) **Blood Pressure and Heart Rate:** Blood pressure and heart rate will be measured once before the gelcap is consumed and once each hour for 4 hours after the gelcap is consumed.
- 4) **Breath Nitric Oxide:** Subjects will exhale into a tube attached to a portable electrochemical analyzer (NIOX VERO, Aerocrine Inc., Morrisville, NC) following the American Thoracic Society/European Respiratory Society guidelines.
- 5) **Saliva Sample:** A sample of saliva will be obtained to determine the different types of oral bacteria residing in the mouth, based on bacterial DNA analyses. Some types of bacteria can convert nitrate to nitrite. This will not be done if the subject participated in Aim 1.
- 6) **Exercise Test – Maximal Muscle Power:** Subjects will complete the following series of tests to assess leg muscle power. A Biodek 4 isokinetic dynamometer (Biodek Medical Systems, Shirley, NY) will be used to measure maximal voluntary force and power during knee extension exercise performed with the dominant leg at angular velocities of (in order) 0, 1.57, 3.14, 4.71, and 6.28 rad/second, which equate to 0, 90, 180, 270, and 360 °/second. The chair back-chair seat angle will be set to 85° and the dynamometer adjusted to place the axis of rotation of the lever arm adjacent to the lateral femoral

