## The Inorganic Nitrate for Exercise in Heart Failure (iNIX-HF) Trial

epicondyle. To minimize other movement, straps will be placed across the torso, hips, and thigh, and subjects will not be allowed to use the handholds. Range of motion will be determined. Next, the subject will perform 3-4 knee extensions at each velocity, with the isometric testing conducted at an angle of 1.22 rad (70°). Two minutes of rest will be allowed after each group of contractions. Strong verbal encouragement will be provided throughout all portions of the isokinetic testing.

- 7) **Exercise Test – Aerobic Capacity:** After 10 min of recovery from the muscle power testing, peak oxygen consumption ( $\dot{V}O_2$ peak) will be determined with an incremental treadmill exercise test to volitional fatigue using the modified Naughton protocol. Subjects will walk on a treadmill and breathe into a mouthpiece while wearing a nose clip (to prevent airflow through the nose). Subjects will be asked to give their maximal effort. Blood pressure and heart rhythm will be monitored. A ParvoMedics TrueOne metabolic cart will be used to measure ventilation (Ve), oxygen consumption ( $\dot{V}O_2$ ), and carbon dioxide production ( $\dot{V}CO_2$ ) throughout exercise. Data from this test will be used to quantify Ve/ $\dot{V}O_2$ , Ve/ $\dot{V}CO_2$ , ventilatory threshold (defined using the V-slope method), oxygen uptake efficiency slope (OUES), and  $\dot{V}O_2$ peak. Subjects will also be asked to give a rating of perceived exertion (RPE) on the Borg scale (6-20) and their perceived dyspnea on a five-point visual-analog scale.
- 8) **KNO3 Gelcaps:** Subjects will receive a 2-week supply of KNO3 gelcaps or placebo gelcaps in a double-blinded manner (i.e., neither the subject nor the investigators will know which gelcap the subject receives).

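### The mouthwash and chewing-gum instruction is tied to KNO3 dose visits, so in Aim 2 it covers the test days at most and leaves the two weeks of home dosing uncovered

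*Combined protocol and SAP*

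**What the plan says.** Mouthwash and chewing gum are mentioned in two places in the supplied text.

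- Methods, Aim 1, Screening Visit, item 6: "Subjects will be instructed to refrain from using mouthwash, antacids, proton pump inhibitors, or chewing gum before each" KNO3 dose visit.
- Aim 1 Sub-Study: Pharmacokinetics, Screening Visit, item 6: "Subjects will be instructed to refrain from using mouthwash, antacids, proton pump inhibitors, or chewing gum before the" single KNO3 dose visit.

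Neither says how long before the visit the restriction starts.

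Aim 2 has no instruction of its own. Its Screening Visit section says: "The screening visit procedures will be the same as for Aim 1 above". It adds: "If a subject participated in Aim 1, then he/she will not have to repeat the screening procedures for Aim 2". Its visits are named Exercise Testing Visit 1 and Exercise Testing Visit 2. Item 8 of the first reads "Subjects will receive a 2-week supply of" active or placebo capsules, and Study Aims gives the regimen as one capsule each morning.

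Two other statements bear on the point. Item 5 of Exercise Testing Visit 1, on the saliva sample, says: "Some types of bacteria can convert nitrate to nitrite". Under Participants, Exclusion, patients on proton pump inhibitors, antacids or xanthine oxidase inhibitors must stop them for the whole study if their physician agrees. The text goes on: "Otherwise patients taking these drugs will be excluded as these can affect reduction of" nitrate and nitrite.

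**The concern.** The protocol treats the conversion of nitrate to nitrite as something to protect. It holds three drug classes study-wide on that ground, and it types oral bacteria from saliva. For a single supervised dose it also restricts mouthwash and gum. In Aim 2, where the placebo comparison rests on two weeks of unsupervised daily dosing, that last safeguard is inherited in wording that fits a different visit structure.

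If mouthwash impairs conversion, it removes effect only where nitrate is given. Equal use in both arms therefore does not cancel: the active-arm response shrinks, the placebo arm is unchanged, and the difference moves toward zero. There is a second consequence. Data Analysis, Aim 2, says that the mean and SD of the pre-to-post change will guide power calculations for a subsequent randomised trial. An understated mean change would carry into that trial's planning.

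**Working it through.** **Step 1. Which days the instruction covers**

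| Period | Covered for mouthwash and gum? | Basis |
|---|---|---|
| Aim 1 dose visits | Yes | Aim 1 Screening Visit, item 6 |
| Pharmacokinetic dose visit | Yes | Sub-study Screening Visit, item 6 |
| Aim 2 testing visits | Arguably | Screening imported from Aim 1; item 3 of Exercise Testing Visit 1 takes vital signs before and hourly after a capsule, so a dose at the visit is implied |
| Aim 2 home-dosing days | No | No text found |
| Aim 3, six weeks | No text at all | Aim 3 has an aim statement but no Methods section |

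The instruction also names antacids and proton pump inhibitors. Those are held study-wide under Participants, Exclusion. Mouthwash and gum are not in that list, so the gap is confined to them.

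**Step 2. The plan's own power figure**

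Inputs, from Sample Size Estimation, Aim 2: 10 per group, two-sided alpha 0.05, baseline VO2peak 22.5 with SD 5.5 mL/kg/min, detectable increase 32.4% at power 0.8.

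- Difference = 0.324 × 22.5 = 7.29 mL/kg/min
- Standardised difference d = 7.29 / 5.5 = 1.325
- Two-sample t-test power (noncentral t) = 0.800; the plan states 0.8, so the figure reproduces.

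**Step 3. What dilution would do, by assumption**

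The documents give neither a usage rate nor a size of loss. Suppose that a fraction f of the mean effect is lost, for example because a share f of active patients gets no effect at all. Then d becomes 1.325 × (1 − f).

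| f | d | Power, 10 per group | n per group for power 0.8 | Approximate sample size multiplier, 1/(1 − f)² |
|---|---|---|---|---|
| 0 | 1.325 | 0.80 | 10 | 1.00 |
| 0.10 | 1.193 | 0.71 | 13 | 1.23 |
| 0.20 | 1.060 | 0.61 | 15 | 1.56 |
| 0.30 | 0.928 | 0.50 | 20 | 2.04 |

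If the loss is all-or-nothing within patients, the active-arm variance also rises. Simulating that mixture gives power of about 0.68, 0.55 and 0.44 for f = 0.10, 0.20 and 0.30.

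**Step 4. Dependence on the starting effect**

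The 32.4% is the increase detectable at power 0.8, not a predicted effect. With an illustrative true increase of 10%, d = 0.10 × 22.5 / 5.5 = 0.409 and power is 0.139 undiluted, against 0.107 at f = 0.20. The fall in power therefore depends heavily on the assumed effect, whereas the proportional shrinkage of the mean difference is f in every case. These figures also use the baseline SD, as the plan's own calculation does, while the planned analysis is ANCOVA on the post-treatment value.

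**The case against.** Several points on the other side stand in whole or in part.

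- **Test days may be covered.** Aim 2 imports the Aim 1 screening, says that outcomes are measured with the same methodology, implies a capsule at the visit, and repeats all procedures except the saliva sample at Visit 2. A reader might infer that Aim 2 has no dose visit and so no protection at all; the documents do not support that. Both outcomes are measured at the testing visits, and nothing in the documents shows that mouthwash on earlier home days alters the final test. That limits how sure one can be of harm. It does not put the home days under the instruction.
- **The power loss is not a measurement.** Rate and size of loss are both assumed, and the plan says that Aim 2 is not designed for adequate power. A reader might take the fall from 0.80 to 0.50 as the expected cost; it is only an illustration. The stake that remains is bias in the estimate, including the change carried forward to the next trial.
- **There is partial monitoring.** Plasma nitrate and nitrite and breath NO are measured at both testing visits, which gives some check on poor conversion. They do not record what happened on home days.
- **The mechanism is thin.** The documents say that some bacteria convert nitrate, but not how mouthwash acts. For gum they give no mechanism.
- **Instructions may exist elsewhere.** Consent pages were removed from the supplied text and cannot be checked.

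A reader might also infer that beetroot juice in the placebo arm could mimic treatment, since the Background says of one capsule: "This is roughly the equivalent of two-thirds of a cup of beetroot juice". That is speculative. Nothing suggests that placebo participants would drink it in such amounts, the protocol itself stresses its unpleasant taste, and randomisation should balance background diet on average. It is not part of this point.

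**Conclusion.** The gap is real but narrow. As written, the mouthwash and gum instruction reaches the Aim 2 test days at most. The home-dosing days are uncovered, and participants who skip screening need not be told again. The likely direction of any effect is toward no difference between arms, on the assumption, which is plausible from the protocol's statement on oral bacteria, that mouthwash reduces conversion. The size cannot be derived from the documents; the power figures of 0.71, 0.61 and 0.50 hold only for assumed losses of 10%, 20% and 30% from a 32.4% effect.

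For Aim 3 the absence follows from a larger omission, the missing Methods section, and should not be counted as a separate fault here. The point merits a change because the safeguard already exists and extending it costs almost nothing, not because a large loss has been shown.

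**What to change.** Reconcile the Aim 1 Screening Visit (item 6), the Aim 2 Screening Visit and the two Aim 2 Exercise Testing Visit sections:

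1. State in the Aim 2 text that the existing mouthwash and chewing-gum instruction applies to both arms, before Exercise Testing Visit 1 and throughout treatment until the final test. Starting before Visit 1 also covers the baseline nitrate, nitrite, breath NO and saliva measurements.
2. Require that it be repeated to participants who come from Aim 1 and skip screening.
3. Record any use at the final visit, so that a small or null difference can be read against it.
4. Carry the same line into Aim 3 when its Methods are written.

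The cost is a mild inconvenience to participants, one sentence of instruction and one extra question. No visit, capsule regimen or analysis changes.
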